### Insertion Site Bleeding – Severity Category

1. Has the bleeding stopped?
  - If no, then: “Is the spot of blood greater than the size of a nickel?”
    - If no, then stop.
    - If yes, then **Severe AE**
  - If yes, then: “Is the spot of blood greater than the size of a nickel?”
    - If no, then stop.
    - If yes, then **Severe AE**

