## Risks of CGM

When the wire-like sensor is deployed by the applicator, participants can expect a sensation similar to a needle insertion for a blood draw. Risks of CGM use include discomfort during sensor insertion, along with pain, inflammation, redness, swelling, minor bleeding and minor infection at the sensor insertion site. Participants might also experience these symptoms as a result of contact between the adhesive pad of the sensor and the skin. In rare cases, an infection can spread to other parts of the body.

Allergic reactions can develop in response to the sensor, the adhesive, and other parts of the CGM. If these symptoms occur, participants have the ability to remove the CGM at will and can anticipate that their symptoms will clear up within one week.

The sensor and/or applicator may fracture during use. If a sensor remains in the skin, there is minimal risk to the patient as long as a physician confirms there are no symptoms of infection or inflammation.

Patients will be advised that the investigational sensor, transmitter, and smartphone must be removed before Magnetic Resonance Imaging (MRI), Computed Tomography (CT) scan, or diathermy treatment. The device is MR Unsafe. Participants should not bring any portion of the device into the MR environment. The Dexcom IUO CGM System has not been tested during MRI or CT scans or with diathermy treatment. The magnetic fields and heat could damage the device, causing it to stop displaying glucose readings, display inaccurate glucose readings, or prevent alerts.

Patients will also be advised of CGM system warnings that may affect the proper operation of the device and/or the patient's safety. These warnings will be described in the informed consent and authorization form, and in the informational materials provided to patients when they receive their systems.

Patients will be provided with a phone number for Dexcom Customer Care and Technical Support that has been set up exclusively for patients participating in this study. Staff for this line will be well-qualified to address any potential questions and risks associated with the investigational device. Significant or serious health risks with CGM are not anticipated.

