## 22. Appendix B

### Adverse Events Severity and Relatedness Questions

May 2017

When patients share a complaint, program coaches will identify the complaint in the Anticipated Complaints Guidebook. Based on the complaint type, coaches will then ask questions to determine:

1. Severity of the complaint (e.g., Mild, Moderate, or Severe), and
2. Relatedness of the complaint to the use of program devices (e.g., Not Related, Probably Not Related, Possibly Related, and Probably Related)

Coaches will document answers in the templates provided, including the Adverse Event document.

If the complaint falls in any of the severity categories highlighted in red, the coach will make a “warm transfer” to the study doctor and/or his staff so that the patient can be scheduled for an ancillary appointment.

If the complaint is an emergency, patients will be instructed to call 911.

If a patient has a complaint that is not listed in the Anticipated Complaints Guidebook, the coach can “warm transfer” the patient to the study clinic for guidance. The coach will document as much as possible in Adverse Event document. Follow up with the clinic will determine severity and relatedness.

Coaches will contact the PI when situations arise that are not covered in the Anticipated Complaints Guidebook.

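### In the Appendix B bleeding script, the answer on whether bleeding has stopped never changes the grade, and Severe is the only grade it can return

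*Protocol*

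**What the plan says.** The introduction to Appendix B (Protocol Section 22) has coaches question patients to establish, first, "Severity of the complaint (e.g., Mild, Moderate, or Severe), and" and, second, how related the complaint is to the study devices. On paperwork it adds: "Coaches will document answers in the templates provided, including the Adverse Event document". On referral it says: "If the complaint falls in any of the severity categories highlighted in red, the coach will make a “warm transfer", meaning a handover to the study doctor or his staff.

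The bleeding script begins with "Has the bleeding stopped". Under the answer no, the coach asks "Is the spot of blood greater than the size of a nickel"; the outcomes are "If no, then stop" and "If yes, then Severe AE". Under the answer yes, the coach asks the same size question, with the same two outcomes.

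Elsewhere, Section 12 (Risks of CGM) names "minor bleeding and minor infection at the sensor insertion site" among the risks of wearing the sensor.

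**The concern.** A script that branches on an answer ought to treat the two answers differently somewhere. This one does not, which suggests a drafting slip in one of the branches. The coach collects whether bleeding is continuing and then has no use for it.

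Two of the resulting grades are hard to square with the rest of the appendix. Continuing bleeding with a small spot leaves the script ungraded, while bleeding that has stopped but left a larger spot takes the highest grade available. The lower two grades on the appendix's own scale are never available for bleeding, even though the protocol itself anticipates minor bleeding.

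At stake is the quality of the coach-assigned severity grade for one type of insertion-site event on an investigational sensor and applicator. Bleeding can only be ungraded or Severe, so its severity distribution cannot be compared with that of most other site reactions. A later analysis plan could not recover the grade, because it is assigned during the coach's call.

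**Working it through.** No sample size or error rate is involved, and the plan gives no figure to reproduce. The check is to enumerate the script and compare it with its neighbours.

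**Inputs.** Two yes/no answers from the bleeding script (bleeding stopped; spot larger than a nickel) and the outcome printed for each path.

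**Decision table.** 2 × 2 = 4 answer pairs:

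| Bleeding stopped? | Larger than a nickel? | Printed outcome |
|---|---|---|
| No | No | Stop, no AE grade |
| No | Yes | Severe AE |
| Yes | No | Stop, no AE grade |
| Yes | Yes | Severe AE |

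Rows 1 and 3 have the same outcome, and so do rows 2 and 4. With spot size held fixed, changing the first answer changes nothing. The four pairs give two distinct outcomes. Two of the four pairs produce a grade, and it is Severe both times. One of the three grades named in the Appendix B introduction is reachable.

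**Comparison with the other severity scripts.** Appendix B contains eight:

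- Six can return Mild, Moderate and Severe: redness or rash, itchiness, pain or discomfort, swelling, bruising, and broken sensor wire.
- One, infection, can return Moderate and Severe.
- One, bleeding, can return Severe only.

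6 + 1 + 1 = 8. Bleeding is the only script with a single grade. The bruising script is the nearest comparator. It also asks whether the problem is progressing, and there a growing bruise does change the grade, overriding a low score on its first question.

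**Comparison with the risk text.** Section 12 lists minor bleeding as a risk of CGM use. The list of device-associated adverse events in Section 9 does not mention bleeding. Of the text available, then, the Appendix B script is the only place that says how bleeding is graded.

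**The case against.** The strongest case on the other side accepts that the branches are identical but says little follows from it. It has several parts.

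- **The report survives.** A reader might infer that ongoing small bleeding is never recorded. The documents do not support that. Coaches document answers whatever grade results. The bleeding script says stop, whereas the redness, itchiness, pain, swelling and bruising scripts tell the coach in terms not to record low scores as an AE. Stopping ends the grading, not the documentation.
- **There are other routes.** Section 9 has participants report to the clinical research coordinator and has coaches connect patients who report events with that coordinator. The study doctor and staff assess severity there, and Section 6 (Integration with patient care) gives the coordinator the same task. A coach's grade of Severe can therefore be reviewed, and an inflated count of Severe events in the final data is not shown.
- **Transfer cannot be checked.** The handover depends on red highlighting, which is not visible in the text reviewed, and the content of the Appendix C oversight chart is not in that text either. One might infer that a patient with a small ongoing bleed would not be transferred. What can be said is narrower: the script prints no severity category for that patient on which a transfer could rest.
- **No headline figure is affected.** The primary aim is implementation process measures (Sections 3 and 10), and no rate of Severe events is named among the endpoints. It would also be empty to note that one of 100 participants is one percentage point, because that holds for any event.
- **The scale is illustrative.** The introduction offers the three grades as examples, and the infection script also omits Mild. Leaving small bleeds ungraded may be deliberate, given that minor bleeding is expected.

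These points stand, and they limit the concern. None of them explains why the script asks whether bleeding has stopped and then treats both answers alike. The last point could justify a narrower range of grades, but not a branch that has no effect.

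**Conclusion.** The point holds in limited form. As written, the bleeding script's first question has no effect on the grade, ongoing bleeding with a small spot is left ungraded, a resolved larger spot is Severe, and Mild and Moderate cannot be reached. Followed literally, this is a stated rule that assigns grades at odds with the appendix's own scheme; it is not a detail left for another document.

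Its size is structural: four answer pairs reduce to two outcomes, and one grade of three is reachable. Nothing in the documents gives the frequency of bleeding reports or of either disputed combination, so no count or rate of misgraded events is offered. The defect is confined to the coach-assigned bleeding grade and any transfer that depends on it. It does not touch the primary aim.

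The conclusion assumes that the printed wording of the two branches is complete and that any colour coding affects referral rather than the grade itself. It makes no judgement on which grade is clinically right for any of the four situations.

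**What to change.** The sponsor and study doctor should reconcile the two branches of the bleeding script with each other and with the severity scale in the Appendix B introduction. The answer on whether bleeding has stopped should either affect the outcome or be removed from the script. If a narrower range of grades is intended for bleeding, the appendix should say so, so that the script and its introduction agree. Coaches should then be briefed on the revised script. No specific grade, size threshold or referral rule is proposed here; those are for the study doctor.

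The cost is a short revision of one script and a note to coaches.

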### **Insertion Site Bleeding – Relatedness Category**

1. Where is the location of the bleeding?
  - If in the same location as the sensor, then Probably Related
  - If in a location where a sensor was within 2 days, then Possibly Related
  - If in a location where a sensor was 2+ days in the past, then Probably Not Related
  - If in a location where a sensor was never placed, then Not Related

### **Insertion Site Infection – Severity Category**

1. Do you notice signs of infection that include inflammation, drainage, pus discharge and pain?
  - a. If no, then stop
  - b. If yes, on a scale of 1 to 10, where 1 is very little and 10 is severe, how much inflammation, drainage, pus discharge and pain do you have?
    - If 1 – 8, **Moderate AE**
    - If 9 – 10, **Severe AE**

### **Insertion Site Infection – Relatedness Category**

1. Where is the location of the infection?
  - If in the same location as the sensor on your skin, then Probably Related
  - If in a location where a sensor was within 2 days, then Possibly Related
  - If in a location where a sensor was 2+ days in the past, then Probably Not Related
  - If in a location where a sensor was never placed, then Not Related

### **Detached/Broken Sensor Wire – Severity Category**

1. Do you see the sensor wire sticking out of your skin?
  - If no, then stop
  - If yes, then ask: On a scale of 1 to 10, where 1 is very little, and 10 is severe, how would you rate your pain or discomfort
    - If 1 – 7, **then Mild AE**
    - If 8 – 9, **then Moderate AE**
    - If 10, **then Severe AE**

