- There are no expected electrical safety risks as the device has passed the electrical safety tests as per EN45502-1 and EN60601;

- If the subject feels any discomfort during the course of the study, he/she will be able to remove the device immediately (the device is not permanent);
- The device is being used to complement, not replace, self-monitoring of blood glucose meter information, and readings are not intended to be used alone to make diabetes self-management decisions. As with the currently approved device and per intended use of similar technologies, subjects in the study will be instructed not to use the device for diabetes therapy or management;
- Subjects will be instructed to monitor their blood glucose levels as per their usual practice.

Adverse events (AE) associated with the use of the device include pruritus (severe itchiness present 48 hours after removal), erythema (reddening of the skin present 48 hours after removal), and inflammation (swelling and pain, defined as 8 or greater on a 10 point scale 48 hours after removal) where the adhesive touches the skin; local infection at insertion site; and shooting pain located at the site of the sensor (defined as 8 or greater on a 10 point scale). Rarely, the sensor wire will fracture when the sensor is being inserted, worn, or removed. If a sensor breaks and no portion of it is visible above the skin, the participant will be instructed to not remove it and seek medical care from the study doctor and/or his staff.

No serious adverse events (SAE) are expected as a result of participation in this minimal risk study. However, AE and SAE will be monitored in the following ways:

- Participants in the study will be instructed to call the study doctor's clinical research coordinator to report all AE and SAE related to the use of the study devices. The study doctor and/or his staff will assess the severity of any health problems associated with the device, and if needed, see the patient at the study clinic to assure appropriate care.
- Study coaches will listen for any reports of AE or SAE in the course of their communications with participants, and will connect reporting patients with the study doctor's clinical research coordinator so events can be assessed and documented and patients can receive care, if needed.

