### Insertion Site Bruising – Severity Category

1. On a scale of 1 to 10, where 1 is very little, and 10 is severe, how much bruising do you have?
  - If 1-5, do not record as AE, **unless the bruise is getting bigger, see question 2**
  - If 6-7, Mild AE
  - If 8-9, Moderate AE
  - If 10, Severe AE
2. Is the bruise or bump getting bigger?
  - If no, stop
  - If yes, **Moderate AE**
  - If yes and bruise is significantly getting bigger, **Severe AE**

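### The coach's severity script for a broken sensor wire ends without a grade or a transfer when no wire is visible, which is the case Section 9 sends to the study doctor

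*Protocol*

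**What the plan says.** Section 9 (Assessment of Safety) lists wire fracture among the device events: "Rarely, the sensor wire will fracture when the sensor is being inserted, worn, or removed". It then gives a rule for one form of it: "If a sensor breaks and no portion of it is visible above the skin, the participant will be instructed to not remove it", and the participant is to seek care from the study doctor or his staff. Section 12 (Risks of CGM) adds a condition: "If a sensor remains in the skin, there is minimal risk to the patient as long as a physician confirms" that there is no sign of infection or inflammation.

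Appendix B holds the questions coaches use to grade complaints. Its introduction sets the transfer rule for listed complaints: "If the complaint falls in any of the severity categories highlighted in red, the coach will make a" direct transfer of the call to the study doctor or his staff. The script for a detached or broken wire begins "Do you see the sensor wire sticking out of your skin". If the answer is no, the script ends. If it is yes, a pain score of 1–7 is a mild event, 8–9 moderate and 10 severe.

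**The concern.** The script grades the wire that can be seen and drops the one that cannot, while Section 9 reserves its explicit instruction for the wire that cannot be seen. A coach who follows the script for that patient reaches the end with no severity category, and so with no severity-based prompt to transfer the call.

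At stake is how one named safety event with an investigational device is handled. A patient with a retained fragment and no symptoms would depend on the coach remembering general duties stated elsewhere, or on the patient remembering the instruction to leave the wire alone and seek care. The event might also go ungraded in the adverse event record. No endpoint or analysis is touched.

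**Working it through.** The plan states no figure to reproduce here. The check is a trace of the script's logic against the other sections, with two simple counts.

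**End points of the broken-wire script (Appendix B)**

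| Wire visible? | Pain score | Result |
|---|---|---|
| Yes | 1–7 | Mild |
| Yes | 8–9 | Moderate |
| Yes | 10 | Severe |
| No | not asked | Script ends, no grade |

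Three of the four end points carry a grade, and all three need a visible wire. The transfer rule works on severity categories. The fourth end point has none, so the rule cannot fire. The red highlighting is lost in the text available, but this does not matter, because the branch has no category to highlight. Appendix B also allows a transfer for complaints missing from the Anticipated Complaints Guidebook. A broken wire has its own script and so appears to be a listed complaint, which means that fallback does not clearly apply.

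**What a negative answer means here.** The coach is in this script because a detached or broken wire was reported. A patient who sees no wire may have removed it whole or may have a fragment under the skin. Visibility is the only thing asked, so both patients leave by the same exit.

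**Comparison with the other stopping branches in Appendix B**

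| Script | Branches that stop | What the answer means |
|---|---|---|
| Skin redness or rash | 1 | No pain or itch |
| Bruising | 1 | "Is the bruise or bump getting bigger" answered no |
| Bleeding | 2 | Blood spot no larger than a nickel |
| Infection | 1 | "Do you notice signs of infection that include inflammation, drainage, pus discharge and pain" answered no |
| Broken wire | 1 | No wire visible; a fragment may remain |

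Total: 1 + 1 + 2 + 1 + 1 = 6. In five of the six the sign is absent, small or not growing. Only the broken-wire branch contains a case that the protocol elsewhere sends to medical care.

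**Exposure.** Inputs are 10 weeks of use (Section 6, Program Length), a 10-day sensor life (Section 6, Program devices) and 100 participants (Section 7).

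- Days per participant: 10 × 7 = 70
- Sensors per participant: 70 / 10 = 7
- Planned wears: 7 × 100 = 700

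This is a ceiling that assumes everyone completes the full 10 weeks. The protocol calls fracture rare and gives no rate, so no expected number of fractures can be derived.

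**The case against.** The best defence is that the script only grades severity and does not set the care pathway. Ending the severity questions is not an order to withhold referral: in the redness script, the same instruction can follow a redness score already graded severe. Section 9's rule is addressed to the participant, and nothing in Appendix B cancels it.

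Referral also has routes that need no grade. Section 9 has coaches connect patients who report an event with the study doctor's "clinical research coordinator so events can be assessed and documented and patients can receive care, if needed". It also tells participants to call the coordinator themselves, and passes reports made to the manufacturer's support line on to the coordinator. Section 6 (Integration with patient care) has the coach help any patient with a possible study-related health concern to reach the study doctor. Section 8 tells patients with device-related medical concerns to contact him. Pain, swelling and infection have their own scripts. The Guidebook and Appendix D are not shown and could hold the missing instruction.

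Much of this stands. It shows that the protocol does not leave the patient without any route to care, and that the text at hand supports only the statement that this script gives no prompt. It also confines the gap to a retained fragment without gradable symptoms, reported to a coach who does not apply the general duties. The comparison of stopping branches is also slightly generous, since one of the bleeding branches follows bleeding that has not yet stopped.

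It does not close the gap. The other routes are general, rely on the patient's initiative, or need symptoms. Section 12 asks a physician to confirm that there are no symptoms, and a patient's failure to report any is no substitute. Material not shown might add an instruction, but it would not correct this branch.

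**Conclusion.** The point holds and should be fixed. The broken-wire script gives no grade and no severity-based transfer for a break with nothing visible, which is inconsistent with Section 9 and with the condition in Section 12. The size is one branch of one script: one of its four end points, and the only one of six stopping branches in Appendix B that takes in a case named for medical care. Up to 700 sensor wears are exposed to an event the protocol calls rare, and no fracture count is claimed.

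The conclusion assumes that a broken wire is a listed complaint, and that stopping means the end of the severity questions and not a bar on referral. Confidence is moderate, because general duties may catch the case and some coach guidance is not shown.

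**What to change.** Change only the negative branch of the broken-wire severity script, so that it reads in substance:

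- If no wire is visible, ask whether the whole wire came out with the sensor.
- If yes, stop.
- If no or not sure, tell the patient not to try to remove it, transfer the call directly to the study doctor or his staff, and record the report in the Adverse Event document for assessment.

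The visible-wire branch stays as it is. The script then has five end points, one of which handles the break that cannot be seen. A bare cross-reference to Section 9 would be cheaper, but it would not separate a wire that came out whole from a retained fragment.

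The added question, the coach's transfer and the referral of unsure patients go somewhat beyond what Section 9 strictly requires. The cost is one line of script, one extra question when no wire is seen, a short note to coaches and a few more study-doctor contacts. The protocol gives no rate for those contacts. If 0.1% to 1% of wears led to such a call, which is purely an assumption, the addition would be 700 × 0.001 = 0.7 to 700 × 0.01 = 7 contacts over the whole study.
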